4.2.7 Safety Populations

The safety population (SAFETY) consists of all ITT subjects who are administered at least one pill/tablet of the delivered study drug (HCQ or placebo). If the delivered study drug differs from the randomly assigned study drug, analysis of the safety population by arm will be according to drug delivered rather than drug assigned. In addition, a post-hoc decision was made to include one person who was erroneously administered study treatment before consenting/randomization due to a participant mix up, so although this individual will be omitted from the study's ITT-based analysis for the primary manuscript, the person will still be considered to be in the safety population for the treatment arm that corresponds to the delivered study treatment. The principal safety analyses for outcomes will be on the ITT population, while the principal analyses for adverse events will be on the SAFETY population. Adverse event summaries will also be prepared for the ITT population or as requested by the DSMB.

5 GENERAL ISSUES FOR STATISTICAL ANALYSES

5.1 Analysis Software

Analysis will be performed using SAS® Software version 9.4 or later whenever possible. Other software packages, including R and StatXact®, may be used for particular specialized procedures. Because of its specialized options for sequential regression imputation, IVEware is preferred for generating multiple imputations.

5.2 Methods for Withdrawals, Missing Data, and Outliers

Subjects with incomplete data for a variable needed in an analysis may, for example, be omitted from that analysis or have the last observation carried forward. Which technique is used depends on the analysis, as described later in the SAP.

Rates of missingness in the primary outcome will be compared between treatment arms for the ITT, dITT, and PP populations. If a substantial number of subjects have incomplete data for this outcome, analyses will be conducted to determine factors significantly related

to missingness. The factors assessed would include, at a minimum, assigned treatment arm and true age stratum.

When multiple imputation is employed, it will be performed separately within each treatment arm if possible (by ITT arm for analyses of the ITT population or subpopulations thereof, or, if necessary, by SAFETY arm for analyses of the SAFETY population).

5.3 Multiple Comparisons and Multiplicity

Explicit adjustments for multiple testing will not be applied. The secondary outcome of viral shedding from 1–14, 28 days will be regarded as exploratory unless the primary analysis of the primary outcome is significant.

5.4 Derived and Computed Variables

Definitions of Days For each subject, the day of randomization to treatment arm will be referred to as *DayR*. The day on which study drug is delivered is *DayD1*, with the next day being *DayD2* and so forth. The day 1 daily study assessment is referred to as occurring on *DayA1*; the next calendar day is *DayA2*, and so forth through *DayA15 = DayA1 + 14*. Note that if the baseline study assessment were to occur on the same calendar day as *DayA1*, the form name in the database will be used to distinguish in such instances which values are used for baseline values and which are used for *DayA1* values so that both sets of measurements can still be utilized. It is expected that for most subjects study drug will be delivered one day after randomization, i.e., that *DayD1 = DayR + 1*. It is also expected that for most subjects *DayD1 = DayA1*. However, because these relationships are not guaranteed, separate nomenclature is sometimes used to define outcomes (typically based on intervals beginning at *DayR*) and study assessments (often based on days since drug delivery or assessment day). Note that while 28-day symptom and quality of life assessments will be considered to be on *DayA28*, there is an allowed –2 day/+2 week window for when they occur. Likewise, the 6-month symptom and quality of life assessments for analysis purposes will use a –2 week/+2 month window. If a randomized subject never provides a daily assessment, such that the anchoring event for defining *DayA1* is unavailable, the convention will be taken to assume *DayA1 = DayR + 1*. Likewise, if study drug delivery date is not available, then it will be assumed that *DayD1 = DayR + 1*. Because swabs are intended to be delivered along with study drug, the drug delivery date will be assumed to correspond to swab delivery date, with the first swab to be collected on *DayD1*. There is likewise a window permitted for the Day 28 swab, although it is narrower: *DayR + 26 to DayR + 30, inclusive*.

Participants may complete surveys late (e.g., slow response by email) or dates may be incorrectly entered that suggest assessments were done early. Additionally, surveys may be completed one day late by phone. It will be assumed that answers to any survey submitted 1 day before or after the intended day for the survey will be treated as the intended day. For example, if the day 4 and day 5 assessments are each completed by email four days after *DayD1*, it will be assumed that the day 4 responses pertain to *DayD4* and the day 5 responses pertain to *DayD5*. However, surveys submitted more than one day before or after the intended day will not be analyzed (except for baseline surveys, which have a longer window because they may be done any day between randomization and the study treatment delivery, inclusive, day 28 surveys, which have a -2 days/ $+2$ weeks window, and 6 month surveys, with a window of -2 weeks/ $+2$ months). Swabs will be analyzed based on the collection date reported by the participant, which may not necessarily match the day on the swab label. If multiple swabs from a participant have the same participant-reported collection date but different results, a positive result will supersede a negative result, and a negative result will supersede an invalid or indeterminate result. If collected swab dates are clearly erroneous (e.g., before day of randomization), the associated swabs will be ignored. If a swab was collected within ± 2 days of *DayR* $+ 28$, it will be regarded as a Day 28 swab.

Primary Outcome Duration of viral shedding (through 14 days after randomization, i.e., *DayR* $+ 14$): this is an integer outcome which is defined as (Date of first sustained negative swab (ignoring any swab that was not in the interval *DayR* $+ 1$ through *DayR* $+ 14$, inclusive) - *DayR*). The date of first sustained negative swab is the first day with a negative swab followed by the next available day's swab being negative. The requirement for confirmation will be waived for patients who are negative for shedding on *DayR* $+ 14$. If no more positive swabs nor negative swabs are available by *DayR* $+ 14$ following a negative swab, the date of the negative swab will be considered confirmed for the primary analysis (using the last-observation-carried-forward approach). If the final swab from on or before *DayR* $+ 14$ which has a positive or negative result is positive and there were not two preceding consecutive negative swabs, the duration will be considered to be right censored on the day of the positive swab.

The primary outcome was viral-shedding duration over the first two weeks. Because the protocol stipulated that swabs would not be obtained during hospitalizations, and that positive results would be carried forward through hospitalization, swab status was considered positive for all hospital days. Hospitalizations or swabs documented after day 15 (i.e., *DayR* $+ 14$) were not used for this outcome. Duration was considered to end on the first day of two consecutive negative swabs, allowing days without swab results between two negative swabs, or on the last available swab result if negative. Without negative confirmation, the outcome was considered right-censored on the day of their last positive result or day 15. In a sensitivity analysis, we treated hospitalized patients prior to day 15 without a prior confirmed

negative as right-censored on the day of hospital admission or day 15.

Also of note is that we assumed all participants were positive on the day of randomization, even if a negative swab were available. It was uncommon for a swab to be available on the day of randomization.

Hospitalization within 14 days of enrollment Hospitalization within 14 days: this is a binary outcome which is “yes” if (a) medical chart review (e.g., performed on *DayD28*) reveals a hospitalization from *DayR* to *DayR+13* (inclusive) or (b) a study assessment reports a hospitalization occurring in this span or (c) the subject is known to have died during this span. If a subjects meets none of these criteria, the outcome will assumed to be “no”. If a subject meets none of these criteria but was lost to follow-up before *DayR+13* and chart review is not permitted because of study withdrawal, the outcome will be considered missing.

Persistence of viral shedding on Day 28 The protocol originally specified a secondary outcome of duration of viral shedding for days 1–14 and 28. Because the primary outcome is viral shedding from *DayR + 1* through *DayR + 14*, the secondary outcome of persistence of viral shedding on Day 28 is substituted for duration through Day 28; there is limited precision between Days 15 and 28. The definition of the persistence of viral shedding on Day 28 outcome relies heavily on the Day 28 swab and is limited to those who have a test result for the Day 28 swab or who are not known to have died on or before *DayR + 30* (there is a ± 2 day window for collecting the Day 28 swab). If the Day 28 swab result is known, the result will be used to define the outcome (“yes” if positive, “no” if negative). Otherwise, subjects with a confirmed cessation of viral shedding when considering daily swab results from *DayR + 1* to *DayR + 25*, inclusive (with the requirement for confirmation waived if the latest available daily result in this interval is negative), and a missing Day 28 value will be assumed to be negative on Day 28; otherwise subjects hospitalized on any of the days *DayR + 26*–*DayR + 30* with a missing Day 28 value will be assumed to be positive on Day 28; otherwise, multiple imputation will be performed as described in Section 7.3.3.

Average of Core COVID-19 symptoms There are seven core symptoms: fever, chills, cough, tiredness, shortness of breath, diarrhea, and muscle aches. Symptoms are measured on a 6-point ordinal scale (not experiencing=0, extremely mild=1, mild=2, moderate=3, severe=4, extremely severe=5) at baseline, days 1–15, and day 28. If at most one of the core symptoms is missing for an assessment, the mean of the non-missing core symptoms’ levels for that assessment will be calculated to obtain a symptom burden score. If two or more core symptoms are missing from the assessment, the average symptom level for that assessment will be considered missing.

Adult Household Contact Viral Acquisition This outcome will be analyzed for households with at least two adults for which no other adult besides the index study subject is positive for COVID-19 at baseline and for which the index study subject is in the ITT population. This binary outcome will be at the household level and will be a “yes” if there is a positive swab by one or more adult household contacts for any of the study-administered swabs from days $DayR + 1$ to $DayR + 14$, inclusive. If there are no positive swabs but at least one negative swab, the outcome will be a “no;” otherwise it will be missing. For some additional analyses, an analogous outcome will be defined at the person level for each non-index adult from a household for which no other adult besides the index study subject is positive for COVID-19 at baseline and for which the index study subject is in the ITT population. Another person-level outcome may count the number of study-administered positive swabs from the person and the number of study-administered swabs with a result (e.g., as an offset in a Poisson regression model), again from days $DayR+1$ to $DayR+14$, inclusive.

As exploratory outcomes, the definitions in the previous paragraph will also include study-administered swabs after $DayR + 14$ through $DayR + 30$, if available).

Exploratory/Safety Outcomes Duration of COVID-19 symptoms (through $DayA15$): this is an integer-valued outcome which is defined as (Date of first sustained asymptomatic day - Start date). To determine the end date, first each symptom assessment from baseline through $DayA15$, inclusive, will be classified as symptomatic, asymptomatic, or unknown. A symptomatic day is one in which at least one of the core symptoms (and the average of the non-baseline symptom levels for that symptom that day, if multiple non-baseline, non-missing symptom levels were provided for that symptom that day) is observed to exceed the permissible threshold: not experiencing fever and chills; extremely mild for shortness of breath, diarrhea, and muscle aches; mild for cough and tiredness. If at most one symptom level is missing on a given day and all observed core symptoms' levels are at or below the permissible threshold, the day will be classified as asymptomatic. Otherwise (i.e., if at most five of the core symptoms have a reported symptom level and none of the reported symptom levels exceeded the threshold), the day will be considered unknown.

The analysis of this outcome is limited to participants whose status on the day of the baseline assessment is symptomatic, per the definition above. The start date is the date of the baseline assessment. The end date (i.e., date of the first sustained asymptomatic day) is the first asymptomatic day which is followed by the next known day being asymptomatic. The requirement for confirmation will be waived for subjects whose last available status as of $DayA15$ was asymptomatic, provided they were not subsequently hospitalized or deceased on or before $DayA15$; the date of the asymptomatic status will be considered confirmed. If the final day with known status from baseline through $DayA15$ is symptomatic and there were not two preceding consecutive asymptomatic days, the duration will be considered to

be right censored on the final symptomatic day (up through and including *DayA15*).

If a subject dies on or before *DayA15* before a confirmed asymptomatic day, the end date will be censored on *DayA15*. If a subject is hospitalized on or before *DayA15* before a confirmed asymptomatic day, the subject will be regarded as symptomatic through the date of discharge or *DayA15*, whichever comes first, which may push the date of censoring back.

Although the protocol mentioned analysis of the symptom duration through Day 28, daily symptom level assessment ceases on *DayA15*. Therefore, the *DayA28* symptom assessments will be ignored when determining symptom duration.

- EQ-5D-5L measures (administered at baseline, 28 days, and 6 months)[1, 2]
 - Visual Analog Scale: 0 to 100 scale. If the value is missing because the individual is known to be deceased when the assessment was to have occurred, the VAS change since baseline will be post-processed to -101 (i.e., worse than possible for any survivor) after multiple imputation (see Section 7.4.5).
 - Index measure: The index measure will use coefficients from the cTTO Model (Model 1 in Table 2 of [2]) to provide a univariable summary of the five component dimensions. If the value is missing because the individual is known to be deceased when the assessment was to have occurred, the index measure will be set to 0. Otherwise, if any of the five dimensions are missing, the index measure will be regarded as missing.
- PCL-5 Total (baseline, 28 days, and 6 months): The 20 items are scored as 0–4 each, producing a total from 0–80.[3] The cited reference does not provide specific guidance on what percentage of missing values may be imputed with the mean of the corresponding non-missing values. In the absence of such a recommendation, if no more than 4 (i.e., 20%) of the relevant items are missing for an individual's total, then the average of the individual's observed item scores from the total will be substituted for the missing items to impute the total. If more than 4 items are missing, the total will be regarded as missing. In addition, subtotals of potential interest may be considered: cluster B (items 1–5), cluster C (6–7), cluster D (8–14), and cluster E (15–20); see [3]. Up to 20% of missing values within a cluster would be imputed with the average of the observed scores in the cluster for determining these subtotals. If the value is missing because the individual is known to be deceased when the assessment was to have occurred, the PCL-5 change since baseline will be post-processed as 81 (i.e., worse than possible for any survivor) after multiple imputation; similar adjustments will be made for cluster subtotals.
- GAD 7 Total (baseline, 28 days, and 6 months): The 7 items are scored as 0–3 each, producing a total from 0–21.[4] The cited reference does not provide specific guidance

on what percentage of missing values may be imputed with the mean of the corresponding non-missing values. In the absence of such a recommendation from this source, if no more than one of the relevant items are missing for an individual's total, then the average of the individual's observed item scores from the total will be substituted for the missing items to impute the total. If more than one item is missing, the total will be regarded as missing. If the value is missing because the individual is known to be deceased when the assessment was to have occurred, the GAD-7 change since baseline will be post-processed to 22 (i.e., worse than possible for any survivor) after multiple imputation.

- PHQ-9 Total (baseline, 28 days, and 6 months): The 9 items are scored as 0-3 each, producing a total from 0-27.^[5] Several scoring approaches are noted, such as treating missing item scores as 0 to be “diagnostically conservative” or mean-imputing up to 20% of item scores.^[5] Another validation article allowed 2 of the 9 items to be mean-imputed.^[6] The latter approach will be used such that up to 2 items may be mean-imputed. If the value is missing because the individual is known to be deceased when the assessment was to have occurred, the PHQ-9 change in total since baseline will be post-processed to 28 (i.e., worse than possible for any survivor) after multiple imputation.
- Hospital admission by 6 months: this is a binary outcome which is “yes” if (a) the secondary 14-day hospitalization outcome is yes, or (b) any hospitalization, for any cause, is found in either the 28-day or 6-month chart review or from subject self-report, or (c) the subject is known to have died by the time of the 6-month chart review. This is “no” otherwise, assuming an absence of documentation of hospitalization in the medical chart is “no.”
- Mortality by 14 days: all-cause mortality at *DayR+13*
- Mortality by 28 days: all-cause mortality at *DayR+27*
- Hospital admission by 28 days: this is a binary outcome which is “yes” if (a) the subject self-reported a hospitalization beginning between *DayR* and *DayR+27* inclusive, or (b) 28-day chart review discovered a hospitalization in this interval, or (c) the subject is known to have died during this interval.
- Post-randomization hospitalizations on or before day of study drug delivery (truncated at *DayR + 13*): this outcome will be assessed for the entire ITT population. This is “yes” if a hospitalization (or death) is documented to have occurred after the time of randomization and *on or* before the earlier of the day of drug delivery (*DayD1*) or (*DayR + 13*). This is “no” otherwise, assuming an absence of documentation of hospitalization/death in the medical chart is “no.”

Subgroup Variables Age group will be determined based on the individual's age at randomization. The age groups will be 18–44, 45–59, 60–74, 75+.

Presence/absence of comorbidity The analysis and/or imputation models of some outcomes utilizes a dichotomous comorbidity variable. Presence/absence of comorbidities will be defined as “Yes” if any of the following are indicated on the medical history form (and “No” otherwise, including if status is not available):

- Diabetes mellitus
- Hypertension
- Chronic pulmonary disease
- Immunocompromised status
- Cardiovascular disease
- Congestive heart failure
- Chronic kidney disease
- Active malignancy
- Cerebrovascular disease
- Chronic liver disease
- Morbid obesity
- Chronic neurological disease

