- Section 5.4: Added definition of assessment days and defined how to handle drug days and assessment days if the anchoring events (drug delivery and assessment surveys) are not available. Corrected censoring explanation for symptom duration to censor on last *symptomatic* day, as applicable. Added definition of comorbidity presence/absence.
- Section 7.1: Added the SAFETY population as a component of the CONSORT-like diagram. Clarified that footnotes may be used to describe some populations.
- Section 7.3.2: Modified to include all 15 daily assessments in defining the univariate average symptom level outcome. Further restricted imputation and analysis to individuals who are not known to have been hospitalized or died on or before *DayA15*, and who have at least one day with a non-missing average symptom level for *DayA1–DayA15*. Previous restriction had specified those not meeting the primary outcome or died within 14 days.
- Section 7.3.3: Moved what had been described in Section 7.4 as *Viral shedding at DayD28* to this section. This reflects the substitution of a secondary outcome from *viral shedding duration through Day 28* to *persistence of viral shedding on day 28*.
- Section 7.4.1: Added a sensitivity analysis for symptom duration that assumes symptom resolution on the first asymptomatic day, regardless of subsequent symptom levels. Also emphasized the departure from the originally specified outcome in the protocol which also considered the Day 28 measurements.
- Section 7.4: Reinserted numerical viral shedding values as an exploratory outcome and described a tentative analysis plan.
- Section 7.5: Stated when safety (rather than per-protocol) and intent-to-treat populations would be used for safety analyses.

Batch of changes for preliminary version of 22 July 2020

- Section 2.1.3: Explained the change from a secondary outcome of *Duration of viral shedding, measured on days 1-14 and 28* to *Persistence of viral shedding on day 28*.
- Sections 5.4, 7.3.3: Described when and how missing Day 28 viral shedding values will be assumed positive or negative, with other values imputed unless the participant has died on or before *DayR + 30*. Explained there is a window for obtaining the Day 28 swabs.

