7.4.4 Hospitalizations before *DayD1*

For this outcome, the frequency and percentage of ITT subjects who are hospitalized or die on or before the earlier of the day before study drug delivery and *DayR* + 13 will be calculated, overall and by treatment arm.

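### For ITT participants never delivered study drug, the SAP's default delivery day closes the pre-drug hospitalization window at DayR + 1 (5.4) or DayR (7.4.4), so later admissions score no (minor)

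*SAP*

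**What the plan says.** Four parts of the SAP bear on this.

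- **Delivery day (SAP 5.4, Definitions of Days).** "The day on which study drug is delivered is" DayD1. For most participants it is expected to be DayR + 1. A default follows: "if study drug delivery date is not available, then it will be assumed that" DayD1 = DayR + 1. The default is introduced as a parallel to the preceding sentence, which sets DayA1 = DayR + 1 for a participant who never gives a daily assessment.
- **Outcome definition (SAP 5.4, Exploratory/Safety Outcomes).** On post-randomization hospitalization up to drug delivery, the SAP states that "this outcome will be assessed for the entire ITT population". A hospitalization or death scores yes when it "is documented to have occurred after the time of randomization and" falls on or "before the earlier of the day of drug delivery" and DayR + 13. Everything else scores no.
- **Outcome analysis (SAP 7.4.4).** The plan reports the frequency and percentage, overall and by arm, of ITT subjects who are "hospitalized or die on or before the earlier of the day before study drug delivery and" DayR + 13. This window ends one day earlier than the one in 5.4. SAP 2.1.4 also lists the outcome as admissions within 14 days of randomization that precede the delivery day.
- **Populations (SAP 4.2.4 and 4.2.5).** Participants stay in ITT whether or not they received any dose. The drug-delivered ITT population (dITT) is the subset to whom the assigned drug was delivered, so the SAP expects that some ITT members may have had no delivery.

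**The concern.** The default day and the outcome window do not fit together for a participant who was never delivered drug. The outcome is meant to pick up admissions and deaths before drug arrived. Someone who is admitted a few days after randomization, and for that reason never gets a kit, fits the description in SAP 2.1.4. Yet the default assigns that person a delivery on DayR + 1, the window closes there or one day sooner, and the admission scores no.

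The error runs one way: it can only turn a yes into a no. It falls on participants whose lack of exposure is least in doubt. At stake is the accuracy of one by-arm count. Dual programming (SAP 5.5) need not catch it, because both programmers may correctly follow the same written rule.

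**Working it through.** The documents give no figure to reproduce: neither the number of participants without delivery nor an expected count for this outcome. The check is to apply the scoring rule day by day.

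**Inputs**

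- d = days from DayR to the first admission or death, from 0 to 13. On d = 0 only events after the time of randomization count (SAP 5.4).
- k = days from DayR to DayD1. With no delivery date, k = 1 by the default in SAP 5.4.
- Rule in 5.4: yes if d ≤ min(k, 13).
- Rule in 7.4.4: yes if d ≤ min(k − 1, 13).

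**Participant never delivered drug**

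| Rule | Limit | Scores yes | Scores no |
|---|---|---|---|
| 5.4 with the default | min(1, 13) = 1 | d = 0, 1 (2 of 14 days) | d = 2 to 13 (12 of 14) |
| 7.4.4 with the default | min(0, 13) = 0 | d = 0 (1 of 14) | d = 1 to 13 (13 of 14) |
| No DayD1 assigned, window to DayR + 13 | 13 | d = 0 to 13 (14 of 14) | none |

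For example, an admission on DayR + 3 scores no under both written rules, since 3 > 1 and 3 > 0. It scores yes when no delivery day is assigned, since 3 ≤ 13. These are counts of calendar days, not shares of admissions; the documents do not say how admissions spread over the 14 days.

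**Participant with a recorded late delivery**

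Here k is the true delivery day. An admission before delivery has d ≤ k − 1. With d at most 13, it scores yes under both rules, so the problem does not reach this group.

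**Effect of the truncation**

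The DayR + 13 limit changes the window only when k > 13 in 5.4, or k − 1 > 13 in 7.4.4. With k fixed at 1 it never does so for a never-delivered participant. It is left to serve only real deliveries more than 13 or 14 days after randomization, although most deliveries are expected on DayR + 1.

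**Does the default reach never-delivered participants?**

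The wording makes no exception. The parallel sentence on assessments deals with an event that never happened, not with an unrecorded date. The SAP's change log describes the addition as covering what to do "if the anchoring events (drug delivery and assessment surveys) are not available", which speaks of events. The log serves here only as evidence of purpose; the current text of 5.4 is what produces the result.

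**The case against.** The strongest reply is that an unavailable delivery date can mean a delivery whose date was not recorded. On that reading a never-delivered participant has no DayD1, the earlier of the two limits falls back to DayR + 13, and the score is right. The truncation supports this: the authors revised it in SAP Version 1.3, and never-delivered participants are the main group it could serve. This is probably what the authors intended. But the SAP does not say so, and the rule it does state supplies a date whenever none is available. A programmer who follows the text gets the wrong score.

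A second reply is that exposure is visible elsewhere. The dITT population separates out participants without delivery. The participant flow diagram in SAP 7.1 must show ITT, dITT and SAFETY counts with reasons for the losses. SAP 7.5.1 analyses 28-day admission and 14-day and 28-day mortality in both ITT and SAFETY. This stands, and it limits the consequence.

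A reader might also infer more than the documents support:

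- *That all never-dosed participants are affected.* The rule turns on delivery. Someone who got the kit and took no pill has a real DayD1.
- *That every admission before drug arrived is lost.* For the never-delivered, admissions on DayR after randomization still score yes, and so do those on DayR + 1 under 5.4. Recorded late deliveries are scored correctly.
- *That the count serves to separate admissions attributable to drug in the ITT hospitalization comparison.* The SAP gives it no such role. It is exploratory, with no test attached, and a no score also covers everyone who was never admitted.

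**Conclusion.** Read literally, the SAP gives never-delivered ITT participants a delivery day of DayR + 1. A first admission or death on DayR + 2 to DayR + 13 (from DayR + 1 under 7.4.4) then scores no although no drug had arrived. This rests on applying the default to participants with no delivery at all. The wording and its context favour that, but no sentence says it outright for this outcome.

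The number affected cannot be derived from the documents and may be small or zero. A reader might be tempted to assume, say, 1% to 3% of the 400 planned, which is 4 to 12 people. That would have to be the joint rate of never being delivered drug and being admitted or dying in the span. The documents give no such rate, and the protocol (section 6.0) expects relatively few hospitalizations.

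Only this exploratory, descriptive by-arm count is affected. The primary outcome and 14-day hospitalization are anchored to DayR and do not use DayD1. The point is minor: a stated rule that gives a wrong count for a narrow group, and is easily put right.

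**What to change.** In SAP 5.4, limit the DayD1 = DayR + 1 convention to participants whose delivery is confirmed but whose date is missing. For participants never delivered drug, leave DayD1 undefined for this outcome and end the window at DayR + 13.

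Use the same wording for the window in 5.4 and 7.4.4. That edit should also settle whether the delivery day itself is included: 5.4 includes it, while 7.4.4 and 2.1.4 do not. This is a separate one-day difference, and the misclassification arises under either version.

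The cost is about one sentence of text and one line of derivation code. No new data are needed, because delivery status must already be known to build dITT and the flow diagram. The derivation should use delivery status itself rather than dITT membership, since dITT requires that the *assigned* drug was delivered. SAP Version 1.4 was prepared after the primary manuscript had been drafted, so the change should be logged as a late clarification, with the number of participants whose score changes, even if it is zero.
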